- h. History of, treatment for, or evidence of, alcohol or drug abuse within the past 12 months or subjects who have met DSM-V criteria for any significant substance use disorder within the past 12 months from the date of the screening visit

- i. Subjects should be excluded if they have a positive drug screen for drugs of abuse that in the investigator's judgment is medically significant, in that it would impact the safety of the subject or the interpretation of the study results. In addition:
  - (1) Detectable levels of cocaine, amphetamine, and phencyclidine (PCP) in the drug screen are exclusionary. Subjects who are positive for amphetamines, and who are on a prescribed amphetamine medication for an approved indication (e.g. ADHD) will be allowed into the study at the Investigator's discretion. This determination by the Investigator must be well documented in the subject's source medical records. The stimulant dose must be stable 4 weeks from prior to randomization visit until the end of treatment visit occurs.
  - (2) Detectable levels of marijuana in the drug screen are not exclusionary, if in the investigator's documented opinion the subject does not meet DSM-V criteria  for substance use disorder, and the positive test does not signal a clinical condition that would impact the safety of the subject or interpretation of the study results.
- j. Hematologic or solid malignancy diagnosis within 5 years prior to screening. Subjects with a history of localized basal cell or squamous cell skin cancer are eligible for the study if they are cancer-free prior to the screening visit in this study.
- k. Body mass index  $\geq 33.0 \text{ kg/m}^2$
- l. History of gallstones or cholecystectomy

3. Allergies and Adverse Drug Reactions

- a. History of drug or other allergy which, in the opinion of the principal investigator, makes the subject unsuitable for participation in the study.

4. Sex and Reproductive Status

- a. Females of child-bearing potential who are unwilling or unable to use an acceptable contraceptive method or abstinence to avoid pregnancy for the entire study period and for 56 days after the study.
- b. Women who are pregnant or breastfeeding. Women with a positive pregnancy test on enrollment or prior to study drug/medication administration.

5. ECG and Laboratory Test Findings

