- a. Estimated glomerular filtration rate (eGFR) according to the re-expressed abbreviated (four-variable) Modification of Diet in Renal Disease (MDRD) Study equation  $\leq 40 \text{ ml/min}/1.73 \text{ m}^2$
- b. Corrected QT interval  $> 470 \text{ msec}$  (QTc by method of Frederica), at Screening

- c. Left Bundle Branch block
- d. Right Bundle Branch Block with a QRS duration  $\geq$  150 msec.
- e. Intraventricular Conduction Defect with a QRS duration  $\geq$  150 msec.
- f. Serum bilirubin (Total, Direct or Indirect)  $> 1 \times$  ULN (Only abnormal values of between 1-1.5x ULN may be repeated once for confirmation during the screening period)
- g. HbA1C  $\geq 8.0\%$  at screening
- h. AST (SGOT) or ALT (SGPT)  $> 1 \times$  ULN (Only abnormal values of between 1-1.5x ULN may be repeated once for confirmation during the screening period)
- i. GGT  $> 1.5 \times$  ULN (Abnormal values  $> 1.5 \times$  ULN may be repeated once for confirmation during the screening period)
- j. Neutrophil count  $\leq 1000/\mu\text{L}$  (or equivalent).

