#### **4.4 Prohibited Concomitant Medication**

The below medications are prohibited prior to randomization and during the course of this study or as specified.

1. St. John's Wort should not be taken 14 days prior to randomization and throughout the study.
2. Barbiturate-containing products (e.g. Fioricet, Fiorinal, butalbital, phenobarbital) should not be taken 14 days prior to randomization and throughout the study.
3. Modafinil (PROVIGIL®) should not be taken 14 days prior to randomization and throughout the study.
4. Butterbur root or extracts should not be taken 14 days prior to randomization and throughout the study.
5. History of use of ergotamine medications on greater than/equal 10 days per month on a regular basis for greater than/equal 3 months.
6. Use of narcotic medication, such as opioids (e.g. morphine, codeine, oxycodone and hydrocodone) for at least 2 days prior to randomization.
7. Use of all acetaminophen or acetaminophen containing products must be discontinued at least 2 days prior to randomization (acetaminophen < 1000 mg/day is allowed as rescue medication, see Section 5.3.5). During the screening phase (14 to 30 days) use of acetaminophen or acetaminophen containing products at daily dosing levels of greater than 1000 mg/day is prohibited.
8. Use of marijuana is prohibited during the study.
9. Muscle relaxants are prohibited during the study. The use of baclofen is permitted, provided that patients are on stable dosing for at least 8 weeks prior to their randomization visit.
10. Concomitant use of strong CYP3A4 inhibitors with rimegepant is prohibited during the study. If use of a strong CYP3A4 inhibitor is required, such as use of HIV Protease Inhibitors, Hepatitis C protease inhibitors, certain azole antifungals, or clarithromycin, dosing with rimegepant should be stopped. Please see section 17, [Appendix 2](#).

11. Concomitant use of strong CYP3A4 inducers with rimegepant is prohibited during the study. Therefore, the use of carbamazepine during this study will be prohibited. However, patients taking oxcarbazepine for the treatment of their trigeminal neuralgia may continue with their current therapy, provided they have been on stable dosing for at least 4 weeks prior to their randomization visit. Patients on carbamazepine may be transitioned to oxcarbazepine. Similarly, these patients must be on stable doses of oxcarbazepine for at least 4 weeks prior to the randomization visit. Please see section [17, Appendix 2](#).

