9 APPENDICES

9.1 Relevant Protocol Deviations

Relevant eligibility protocol deviations include the following categories:

- A mean of < 4 on the daily “average intensity” score on the NPRS during the last 14 days in the Screening Period
- TN onset less than 3 months prior to Screening
- Classical TN not confirmed on neuroimaging
- Neurological examination not done or incomplete (i.e., cranial, facial, or trigeminal nerve assessment not done)
- Non-compliance with or inability to complete the paper diary during the Screening Period. Non-compliance is 2 or more missed evening reports during the Screening Phase. Subjects should be considered for discontinuation after discussion with the sponsor.
- Medical history, defined as any of the following subcategories:
 - Subjects with Myocardial Infarction (MI), Acute Coronary Syndrome (ACS), Percutaneous Coronary Intervention (PCI), cardiac surgery, stroke or transient focal neurological deficit during the 6 months prior to screening
 - Gilbert’s syndrome or any other active hepatic or biliary disorder
 - Gastric or small intestinal surgery.

Finding out of range during the pretreatment period or Day 35 if entering OL phase, defined as any of the following:

- ALT/AST/Direct Bilirubin/Indirect Bilirubin/Total Bilirubin > 1 xULN
- GGT > 1.5 xULN
- ECG abnormalities as follows:

- Corrected QT interval > 470 msec (QTc by method of Frederica)
- Left Bundle Branch block
- Right Bundle Branch Block with a QRS duration ≥ 150 msec
- Intraventricular Conduction Defect with a QRS duration ≥ 150 msec
- Neutrophil count $\leq 1000/\mu\text{L}$ (or equivalent)
- HbA1c $\geq 8\%$
- Diastolic measurement of $\geq 96\text{mmHg}$
- Estimated glomerular filtration rate (eGFR) according to the re-expressed abbreviated (4-variable) Modification of Diet in Renal Disease (MDRD) Study equation ≤ 40 mL/min/1.73m²
- BMI $\geq 33 \text{ kg/m}^2$
- Positive for cocaine or PCPs at any visit
- Females with a positive pregnancy test at any visit
- Subject's score is > 1 ("a little") on Question 2 or > 0 ("Not at all") on any other question on the Sheehan Suicidality Tracking Scale at any visit

Relevant subject management protocol deviations include the following:

- Type of TN discrepant between IWRS and CRF data, defined as any of the following subcategories:
 - IWRS randomization stratum of "atypical", but CRF Neuralgia type "typical" (Demographics page)

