 - IWRS randomization stratum of "typical", but CRF Neuralgia type "atypical" (Demographics page)
- Prohibited non-study medications, procedures, or therapies defined as any of the following:
 - Standard of care Trigeminal Neuralgia medications with dose change or with start date < 4 weeks prior to randomization (see Section 4.4.1 for the definition of standard of care Trigeminal Neuralgia medication)
 - Carbamazepine taken during the Screening Period or afterward

- St. John's Wort taken up to 14 days prior to the Baseline Visit (randomization) or afterward
- Barbiturate-containing products (e.g. Fioricet, Fiorinal, butalbital, phenobarbital) taken up to 14 days prior to the Baseline Visit (randomization) or afterward
- Modafinil (PROVIGIL®) taken up to 14 days prior to the Baseline Visit (randomization) or afterward
- Butterbur root or extracts taken up to 14 days prior to the Baseline Visit (randomization) or afterward
- Ergotamine medications taken on ≥ 10 days per month on a regular basis for ≥ 3 months
- Narcotic medication, such as opioids, taken up to 2 days prior to the Baseline Visit or afterward
- Acetaminophen or acetaminophen containing products taken within 2 days before randomization.
- Use of acetaminophen during the Screening Period (3 to 14 days) or throughout the study at daily dosing levels of greater than 1000 mg/day
- Muscle relaxants (except baclofen) taken during the Screening Period or throughout the study
- Baclofen with start date < 8 weeks prior to randomization
- Strong CYP3A4 inhibitors taken during the Screening Period or throughout the study
- Strong CYP3A4 inducers taken during the Screening Period or throughout the study
- Strong inhibitors of the P-gp transporter taken during the Screening Period or throughout the study
- CGRP antagonists (biologic or small molecule) taken during the Screening Period or throughout the study

Note: Medications taken up to X days before a reference date or afterward are defined as those with medication start date or stop date \geq reference date $- X$. Refer to the Core SAP for additional details about prohibited non-study medications.

- DB study drug dosing issue, defined as any of the following subcategories (see Section 6.2.6):
 - DB study drug taken but not randomized
 - DB tablet count compliance < 80% from DB study drug start to later of last scheduled DBT Phase visit or DB study drug end
 - > 1 DB tablet taken on any 1 day
 - Incorrect DB study drug taken

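### Three deviation rules in SAP 9.1 differ from the protocol, so the descriptive deviation table can over-count and under-count

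*SAP*

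**What the plan says.** SAP 6.2.4.1 tabulates relevant protocol deviations by treatment sequence and overall for the full analysis set, in the order of SAP 9.1 and including categories with zero counts. A by-subject listing accompanies the table. The rules are in SAP 9.1.

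- **Liver tests.** Under the line "Finding out of range during the pretreatment period or Day 35 if entering OL phase, defined as any of the following", the SAP lists "ALT/AST/Direct Bilirubin/Indirect Bilirubin/Total Bilirubin > 1 xULN" and a GGT limit of 1.5 x ULN. It mentions no repeat. For bilirubin and AST/ALT, protocol 4.3 items 5f and 5h state "Only abnormal values of between 1-1.5x ULN may be repeated once for confirmation during the screening period". For GGT, item 5i says that a value above its limit of 1.5 x "ULN may be repeated once for confirmation during the screening period".
- **Acetaminophen.** Under subject management, the SAP lists "Use of acetaminophen during the Screening Period (3 to 14 days) or throughout the study at daily dosing levels of greater than 1000 mg/day". Protocol 4.4 item 7 has "During the screening phase (14 to 30 days) use of acetaminophen or acetaminophen containing products at daily dosing levels of greater than 1000 mg/day" as prohibited. A separate SAP item covers any acetaminophen in the 2 days before randomisation.
- **Drug screen.** The SAP item reads "Positive for cocaine or PCPs at any visit". Protocol 4.3 item 2i(1) reads "Detectable levels of cocaine, amphetamine, and phencyclidine (PCP) in the drug screen are exclusionary", with an exception at the investigator's discretion for amphetamine prescribed for an approved indication.

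**The concern.** A deviation table tells the reader how far the randomised patients match the intended population and how well conduct rules were kept. It can do so only if each programmed rule tests the protocol's own criterion. The liver rule as printed can report an eligible patient as an eligibility deviation. Protocol 4.6 says that the sponsor grants no eligibility exceptions, so such a flag would read as a site breach. The drug-screen rule, and on one reading the acetaminophen rule, can pass over a real departure. Because zero rows are shown, a zero against the drug-screen item would look like reassurance although amphetamine was never examined.

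**Working it through.** The plan gives no figure to reproduce on this point. The check is a comparison of texts, plus a count of days for acetaminophen.

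**1. Liver tests.** Take a screening ALT of 1.2 x ULN followed by a normal permitted repeat.
- Protocol: 1.2 lies between 1 and 1.5, so item 5h allows one repeat for confirmation. The exclusion is not confirmed and the patient can be randomised. The protocol does not spell out that the repeat decides, but a confirmatory repeat has no other evident purpose.
- SAP 9.1: one pretreatment value exceeds 1 x ULN, so the patient is counted.
- The same conflict arises for bilirubin at 1 to 1.5 x ULN and for GGT above 1.5 x ULN. It does not arise for ALT, AST or bilirubin above 1.5 x ULN, where no repeat is allowed and the flag is right.

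**2. Acetaminophen above 1000 mg/day.** Let L be the length of screening in days; the protocol allows 14 to 30. Read the SAP's 3 to 14 as days before randomisation. Days 3 to 14 are covered by this item, and days 1 and 2 by the separate 2-day item, so unchecked days = L - 14.

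| L | Unchecked days | Share of screening |
|---|---|---|
| 14 | 14 - 14 = 0 | 0% |
| 21 | 21 - 14 = 7 | 7/21 = 33% |
| 30 | 30 - 14 = 16 | 16/30 = 53% |

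The unchecked days are day 15 and earlier, counted back from randomisation. Inclusion criterion 2d and SAP 9.1 itself judge the qualifying pain score on the last 14 days of screening, so every unchecked day precedes that window.

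**3. Drug screen.** The protocol names cocaine, amphetamine and PCP; the SAP names cocaine and PCP. An amphetamine-positive patient with no prescription is excluded by item 2i(1) but matches no category in SAP 9.1.

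**4. Weight of one misclassified patient.** At the planned 60 randomised, 30 per sequence, one wrong entry moves the overall percentage by 1/60 = 1.7 points and a sequence percentage by 1/30 = 3.3 points. SAP 1 says that the study stopped early for low enrolment. With fewer than 60 randomised, each step would be larger.

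**The case against.** The strongest reply on the liver tests is the Core SAP. SAP 1 gives it primacy where this SAP is silent or refers to it directly. SAP 9.1 is silent on repeats, and SAP 6.2.4.1 points to the Core SAP for further details on deviations. A repeat rule may exist there. This stands: the false flag follows from the text supplied but cannot be confirmed as the final programming. A reader might infer that this SAP's own primacy settles the matter, but that primacy does not reach points on which it is silent.

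On acetaminophen, the words about use throughout the study could be taken to include all of screening. The bracketed days could also be meant as the length of the screening period, as in the protocol. On either reading no day is missed and only the conflict in the text remains. Against the first reading, neighbouring SAP items, such as those on muscle relaxants and CYP3A4 inhibitors, name screening and the rest of the study separately.

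On amphetamine, the prescription exception needs judgement that a program may not be able to make. SAP 6.2.4.2 has a separate listing for non-programmable deviations. SAP 9.1 is also a selected list that leaves out other exclusions, such as HIV history and recent malignancy. Omission alone therefore proves little. But here the item exists and names two of the protocol's three substances, and nothing sends the third to the other listing.

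Several stronger readings are tempting but not supported:
- *Day 1 values should not count.* Protocol Table 1 schedules the eligibility check, laboratory tests and liver function tests at Baseline. Items 5f and 5h do not confine their limits to screening, whereas 5b and 5g do.
- *Including HbA1c in the Day 35 check distorts the count.* HbA1c is measured only at screening (protocol 5.2.6, SAP 6.4.2), so that check flags no one.
- *Unchecked acetaminophen use contaminates pain qualification.* The Study Summary and protocol 3.5.2 speak loosely of the whole 14 to 30 days, but the inclusion criterion itself uses the last 14.
- *A single diastolic reading of at least 96 mmHg is plainly the wrong test.* Exclusion 2c offers repeated readings only as an example, so the two wordings need reconciling and no more.

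**Conclusion.** The three mismatches are real on the face of the documents, and the table and listing in SAP 6.2.4.1 can be wrong in both directions. The amphetamine gap is the firmest. The liver-test over-count holds unless the Core SAP has a repeat rule. The acetaminophen gap runs from none to 16 of 30 screening days (53%), and depends on reading 3 to 14 as days before randomisation and on the length of screening.

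The number of patients affected cannot be given. The documents hold no rate of transient liver-test elevations, of amphetamine positives or of early-screening acetaminophen use. A rate built up analyte by analyte would also wrongly treat related tests as independent, since total bilirubin is the sum of direct and indirect.

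The consequence is confined to a descriptive table and listing. A reader might infer a threat to the efficacy results, but the analysis sets in SAP 4.1 do not use deviations, there is no per-protocol set, and SAP 5 says that significance will not be evaluated. The point is worth correcting because it is cheap and the table is meant for the study report. Confidence is moderate, because the Core SAP was not available.

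**What to change.** Reconcile SAP 9.1 with protocol 4.3 and 4.4. No view is taken on what the clinical limits should be; the aim is that the deviation rules test the criteria as the protocol states them.

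- **Liver tests and GGT:** apply the limits after any screening repeat that items 5f, 5h and 5i permit, or cite the exact Core SAP rule that does this. Keep Day 1 values in the check.
- **Acetaminophen:** replace the 3 to 14 days with the screening phase as the protocol defines it, so that no screening day is left out. Leave the item under subject management.
- **Drug screen:** add an amphetamine positive without documented prescribed use. If the exception cannot be programmed, assign these cases to manual review and say so.
- **Diastolic pressure:** reconcile the SAP's measurement wording with exclusion 2c, where repeated readings are an example.

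The cost is a short SAP text change and revised deviation programming on data already collected, with manual review of any amphetamine positives. No new data, analysis set or efficacy analysis is needed.
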